19.6 Unblinding Procedures

Not applicable.

19.7 Stopping Rules

The study will be stopped if one method is found to be clearly superior or if there are adverse reactions.

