3.3 Early Withdrawal of Subjects

3.3.1 Criteria for removal from study

Patients will be withdrawn from the study for safety reasons including severe adverse reactions, failure of subject to adhere to protocol requirements, or subject consent withdrawal.

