3.3.2 Follow-up for withdrawn subjects

The subjects may withdraw at any point prior to the steroid injection. Additionally, they may elect not to participate in rating their pain right after they receive the injections. Subjects who withdraw and prefer to have a lidocaine injection, may still participate in rating their pain after the lidocaine + steroid injection. Any subject who is getting steroid injections for shoulder pain may replace subjects who withdrew.

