10.8 Suspension of research

There will be no stopping rules in this study as all medications are FDA approved and safe for patient use.

If a patient, at any point in the course of their treatment demonstrates a significant adverse event related to the study medication, then the adverse event will be addressed.

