11.0 Risks

Loss of confidentiality will be minimized as the research team will only have access to the research data and all information will be kept in a shared research file in HersheyMed.net on a password-protected computer, in the Orthopaedic research office locked filing cabinets.

Subjects will be assigned to a treatment program by chance. The treatment received may prove to be less effective or to have more side effects than the other research treatment(s) or other available treatments.

Ethyl Chloride - freezing may alter skin pigment

Kenalog - joint tissue damage, swelling in your veins, allergic reaction, infection, increase in blood sugar.

Lidocaine - itching, rash, swelling of the skin, pain at the injection site, numbness, dizziness, and allergic reactions. Rarely, when injected into the blood stream lidocaine can cause confusion, coma, seizures, respiratory arrest, heart beat irregularities, and toxicities; however, in this study lidocaine will not be injected into your bloodstream.

Nerve damage for a period of time after the injection.

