19.0 Adverse Event Reporting

19.1 Adverse Event Definitions

Adverse event	Any untoward medical occurrence associated with the use of the drug in humans, whether or not considered drug related
Adverse reaction	Any adverse event caused by a drug
Suspected adverse reaction	Any adverse event for which there is a reasonable possibility that the drug caused the adverse event. Suspected adverse reaction implies a lesser degree of certainty about causality than "adverse reaction". 
• Reasonable possibility. For the purpose of IND safety reporting, "reasonable possibility" means there is evidence to suggest a causal relationship between the drug and the adverse event.
Serious adverse event or Serious suspected adverse reaction	Serious adverse event or Serious suspected adverse reaction: An adverse event or suspected adverse reaction that in the view of either the investigator or sponsor, it results in any of the following outcomes: Death, a life-threatening adverse event, inpatient hospitalization or prolongation of existing hospitalization, a persistent or significant incapacity or substantial disruption of the ability to conduct normal life functions, or a congenital anomaly/birth defect. Important medical events that may not result in death, be life-threatening, or require hospitalization may be considered serious when, based upon appropriate

	medical judgment, they may jeopardize the patient or subject and may require medical or surgical intervention to prevent one of the outcomes listed in this definition.
Life-threatening adverse event or life-threatening suspected adverse reaction	An adverse event or suspected adverse reaction is considered “life-threatening” if, in the view of either the Investigator (i.e., the study site principal investigator) or Sponsor, its occurrence places the patient or research subject at immediate risk of death. It does not include an adverse event or suspected adverse reaction that had it occurred in a more severe form, might have caused death.
Unexpected adverse event or Unexpected suspected adverse reaction.	An adverse event or suspected adverse reaction is considered “unexpected” if it is not listed in the investigator brochure, general investigational plan, clinical protocol, or elsewhere in the current IND application; or is not listed at the specificity or severity that has been previously observed and/or specified.

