19.3 Causality and Severity Assessments

The investigator will promptly review documented adverse events and abnormal test findings to determine 1) if the abnormal test finding should be classified as an adverse event; 2) if there is a reasonable possibility that the adverse event was caused by the study drug(s) or device(s); and 3) if the adverse event meets the criteria for a serious adverse event.

If the investigator's final determination of causality is “unknown and of questionable relationship to the study drug(s) or device(s)”, the adverse event will be classified as associated with the use of the study drug(s) or device(s) for reporting purposes. If the investigator's final determination of causality is “unknown but not related to the study drug(s) or device(s)”, this determination and the rationale for the determination will be documented in the respective subject's case history.

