19.5 Reporting Adverse Reactions and Unanticipated Problems to the Responsible IRB

In accordance with applicable policies of The Pennsylvania State University Institutional Review Board (IRB), the investigator will report, to the IRB, any observed or reported harm (adverse event) experienced by a subject or other individual, which in the opinion of the investigator is determined to be (1) unexpected; and (2) probably related to the research procedures. Harms (adverse events) will be submitted to the IRB in accordance with the IRB policies and procedures.

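### Section 19.7 stops the trial for any adverse reaction, with no severity floor, while section 10.8 says there are no stopping rules; the two cannot both be followed

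*Combined protocol and SAP*

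**What the plan says.** Two sections of the combined protocol and SAP speak directly to stopping the trial.

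- **Section 19.7 (Stopping Rules):** "The study will be stopped if one method is found to be clearly superior or if there are adverse reactions". It gives no grade, seriousness criterion, count or rate for the reactions.
- **Section 10.8 (Suspension of research):** "There will be no stopping rules in this study as all medications are FDA approved and safe for patient use". It adds that a significant adverse event related to the study medication is to be dealt with, and does not mention halting enrollment.

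The meaning of 19.7 depends on two other places.

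- **Section 19.1** defines an adverse reaction as "Any adverse event caused by a drug". The same table separately defines suspected, serious, life-threatening and unexpected events.
- **Section 11.0** lists the expected effects of one study drug: "Lidocaine - itching, rash, swelling of the skin, pain at the injection site, numbness, dizziness, and allergic reactions". Under section 7.1, all three groups receive 4 ml of 1% lidocaine with the steroid, and Group B is given a further 2 ml under the skin (section 7.4.6.3).

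At the level of the individual patient, section 3.3.1 says: "Patients will be withdrawn from the study for safety reasons including severe adverse reactions".

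**The concern.** Section 19.7 is mandatory and section 10.8 denies that any such rule exists. When a drug-caused event occurs, staff who stop the trial depart from 10.8, and staff who continue depart from 19.7. The threshold actually used would be unwritten, and either decision could later be challenged as discretionary.

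The wording of 19.7 adds a second difficulty. Because 19.1 sets no severity floor, the literal trigger includes minor effects that the protocol itself expects. Applied as written, it could end enrollment early for a trivial reason and leave the pain comparison short of its planned size. If 10.8 is followed instead, there is no prespecified safety trigger at all.

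**Working it through.** **Step 1. The texts side by side, for one drug-caused event.**

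| Event | Section 19.7, using the 19.1 definition | Section 10.8 | Section 3.3.1 |
|---|---|---|---|
| Minor and expected (e.g. itching) | Stop the trial | No stop | Not mentioned |
| Significant or severe | Stop the trial | Deal with the event; no stop | Withdraw that patient |

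The first two action columns conflict in both rows. The third does not conflict outright, because withdrawing one patient does not exclude also stopping the study. A patient-level action for a severe reaction fits better with a trial that goes on, but that is an inference.

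**Step 2. Whether another section supplies the missing threshold.**

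- Section 19.3 has the investigator judge causality and seriousness, but 19.7 does not tie stopping to the seriousness judgement.
- Section 10.6 has adverse events reviewed as they occur, with no action attached.
- Section 19.5 requires reporting to the IRB of harm "which in the opinion of the investigator is determined to be (1) unexpected; and (2) probably related to the research procedures". That is a reporting duty and contains no stopping trigger.

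So the threshold is not supplied elsewhere.

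**Step 3. The planned size, as a reference point.** Section 8.2 gives 50 per group for 80% power, with a difference of 2, SD 3 and a Type I error rate of 1.7% per comparison. A two-sample t-test at two-sided 0.05/3 (sidedness is not stated, so two-sided is assumed) needs 48.6, so 49 per group, and has 81.3% power at 50. The stated figure reproduces and is not in question.

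**Step 4. Illustration of the literal rule.** The documents give no reaction rate, so every rate p below is an assumption.

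- Chance of at least one reaction in 150 subjects: 1 − (1 − p)^150.
- Median subject at first reaction: ln 0.5 / ln(1 − p), rounded up.
- Chance of at least two in 150 (binomial), in case the plural in 19.7 is meant.

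| Assumed p | At least 1 in 150 | At least 2 in 150 | Median subject at first reaction |
|---|---|---|---|
| 0.5% | 52.9% | 17.3% | 139 |
| 1% | 77.9% | 44.3% | 69 |
| 2% | 95.2% | 80.4% | 35 |
| 10% | over 99.99% | over 99.99% | 7 |

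The chance of a stop at the first reaction passes one half at p = 1 − 0.5^(1/150) = 0.46%.

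Dividing the medians 139, 69 and 35 by three gives about 46, 23 and 12 per arm. Power from the t-test in step 3 is then 77.4%, 41.8% and 19.3%. A stop at the median costs little at 0.5% and most of the power at 2%.

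**Step 5. Illustration of a serious-reaction trigger.** With assumed serious rates of 0.01%, 0.05% and 0.1%, the same first formula gives a 1.5%, 7.2% and 13.9% chance of at least one pause in 150 subjects.

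**The case against.** The strongest reply is that no sensible investigator would stop an open-label, one-visit trial of standard-of-care products at the first itch. Safety oversight is not absent: a licensed investigator assesses events (sections 10.1 and 20.1.2), causality and seriousness are judged (19.3), and unexpected, probably related harms go to the IRB (19.5). Observation is also short, with ratings immediately and ten minutes after the injection and no long-term follow-up, so many delayed reactions would not be seen during participation. All of this stands and limits the practical harm. It does not say which of the two sections governs.

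A reader might go further in three ways that the documents do not support.

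- **That section 3.3.2 shows the trial is meant to continue after a severe reaction**, because it says: "Any subject who is getting steroid injections for shoulder pain may replace subjects who withdrew". That section never mentions reactions and is mainly about withdrawal before the injection. It is not evidence on this point.
- **That the trial would probably have stopped early and lost power.** The stop and power figures follow entirely from chosen rates. Rates of 0.5% to 2% do not even match the literal reading, which would count expected numbness and so could fire within the first few subjects. They are also too high for a serious-only reading.
- **That the pain comparison is biased.** If the trial completes, this conflict does not affect it.

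**Conclusion.** The conflict between 19.7 and 10.8 is explicit and unreconciled, and the adverse-reaction trigger in 19.7 has no severity floor. This is a stated rule that is wrong as written, not just a missing detail, and it should be corrected. The conclusion rests on the wording of 19.7, 10.8 and 19.1 alone; 3.3.1 lends support only by inference.

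Its size cannot be put as a number from the documents. The stopping probabilities and power figures above show how sensitive a literal rule would be and carry no weight beyond that. The consequence is ambiguity about when to halt, with early termination for a minor effect as the extreme case.

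**What to change.** **If a safety stop is wanted:**

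1. In section 10.8, delete the sentence denying any stopping rule and refer to 19.7.
2. In section 19.7, replace the adverse-reaction clause with a trigger in terms the protocol already defines: *Enrollment is paused for IRB review after any serious suspected adverse reaction (19.1), as determined by the investigator under 19.3. Non-serious reactions, whether or not listed in section 11, do not stop the study; they are handled under 3.3.1 and reported under 19.5 where applicable.*

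**If no safety stop is wanted:** delete the adverse-reaction clause from 19.7 and reword 10.8 to say that there is no safety stopping rule.

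Neither route settles the superiority clause in 19.7. It has no boundary, error rate or timing, although section 10.6 plans an interim analysis at 50% of enrollment. Referring 10.8 to 19.7 should not be taken to endorse it; it needs its own correction.

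**Cost:** wording in two sections and one IRB amendment, with no extra subjects, visits or data. Under the first route the investigator gives up case-by-case discretion, and a single serious suspected reaction would hold enrollment until the IRB responds.

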20.0 Study Monitoring, Auditing and Inspecting

20.1 Study Monitoring Plan

20.1.1 Quality Assurance and Quality Control

Study data will be recorded and kept in a shared folder on hersheymed.net in a restricted file accessible by investigators on the study. The Principal Investigator will oversee all aspects of the study including monitoring.

20.1.2 Safety Monitoring

The Principal Investigator will confirm that all adverse events (AE) are correctly entered into the AE case report forms by the coordinator; be available to answer any questions that the coordinators may have concerning AEs; and will notify the IRB, FDA, sponsor and/or DSMB of all applicable AEs as appropriate. All assessments of AEs will be made by a licensed medical professional who is an investigator on the research.

The Research Coordinator will complete the appropriate report form and logs; assist the PI to prepare reports and notify the IRB, FDA and/or DSMB of all Unanticipated Problems/SAE's.

The Monitor will confirm that the AEs are correctly entered into the case report forms. The Monitor will also confirm that the adverse events are consistent with the source documents and are reported to the appropriate regulatory bodies as required.

20.2 Data and/or specimens being stored

Regulatory work, paper copies of data, electronic copies of data.

20.3 Location of storage

Paper regulatory work and data will be kept at [name] in locked files.

Electronic data will be kept in hersheymed.net investigator accessible shared files.

20.4 Duration of storage

Data will be kept at least 6 years, and disposed as per the PI.

20.5 Access to data and/or specimens

Data will only be accessible by investigators listed on the study.

20.6 Procedures to release data or specimens

not applicable

20.7 Process for returning results

not applicable

